Brief Title: Peak plantar pressures while wearing a carbon fiber off-loading orthoses

Official Grant Title: Carbon Fiber Off-Loading Orthosis

NCT03618628

Date uploaded to clinicaltrials.gov: 2/11/2019

Date the protocol most recently uploaded to human subjects protection review board: 6/28/2018

Carbon Fiber Off Loading Orthosis

Research Design and Methods

Model Development: A carbon fiber off-loading ankle foot orthosis will be fabricated for a study team member using the geometry consistent with the clinical standard at Orthotic & Prosthetic Design. The complete carbon fiber off loading orthosis (CFO) consisted of the carbon fiber composite (CFC) strut, leather calf support, and a leather and foam shoe. This representative CFO will serve as a baseline from which a finite element (FE) model will be built. The model will then be altered as desired to determine the effects of variable design characteristics.

First, a computed tomography (CT) scan of the CFO will be completed using a Siemens Biograph 40 scanner (0.71 x 0.71 x 0.60 voxel spacing). Individual structures of the CFO will be segmented and reconstructed in 3D. The CFC strut geometry and material properties are the greatest determining factors in CFO stiffness and mechanical performance and were the basis of the FE model. From the 3D reconstruction, the strut geometry will be traced, extruded, and meshed within Abaqus Explicit FE solver software. Thickness measurements of the strut will be confirmed with caliper measurements at various locations along its profile. Ten caliper measurements will be taken to verify the width of the strut. These measurements will be averaged and the traced profile extruded to the averaged value. Doing will keep the FE mesh consistent with the 3D reconstruction geometry but eliminate small geometric artifacts from segmentation of CT images.

The resulting model will be used in the FE analyses to determine deflection and stress responses of the strut under varied loads and with varied CFC fabrication techniques (i.e. layups). Material properties for the CFC and CFC-to-CFC layer interfaces will be derived from the manufacturer specifications and from prior investigations by our group (REF Zou JRRD 2014). Boundary and loading conditions will be imposed on the model to simulate forces applied during a typical gait cycle. Specifically, the top of the strut will be fixed in place and experimentally derived force data (from the subject for whom the CFO will be fitted) will be applied as a time-varying and location-varying vertical force that moved from the heel to the toe in correspondence with the subject's average ground reaction force trajectory during the stance phase of gait. In this way, stress and deflection throughout the strut will be measured throughout the entire step, from initial contact to toe off. These results will be cross referenced with a simple beam bending equation to confirm accuracy. Deflection of the strut will be measured as an indicator of energy return that can be expected in various CFC layups.

Model Execution / CFO Design Characteristic Perturbation: Preimpregnated CFC (prepreg CFC) is composed of a sheet of single layer carbon fibers embedded in resin. This material comes in two forms; one is unidirectional, in which the fibers of a single layer all follow the same direction, while the other is a 2x2 twill, in which the fibers are interwoven at 90 degree angles from each other, with half the fibers going in one direction and the other half going in the transverse direction. During brace fabrication, layers of CFC are added one at a time in varying directions depending on in which direction strength is needed.

During the course of this award, three CFC layups will be explored. The different layups were chosen after review of manufacturing techniques at Orthotic & Prosthetic Design prior to the award, review of existing literature, review of prior modeling results from our group, and through conversations with the CFC manufacturer. The goal of exploring the three layup schemes was to find the layup that 1) maximized deflection of the brace (i.e. indirect measure of energy return), while simultaneously 2) minimized stress within the brace (i.e. indirect measure of propensity for strut fracture and failure). The three CFC were each modeled with the same geometry (equal length and thickness), boundary conditions, and loading conditions.

Layup A: Unidirectional fibers, two out of every three layers were oriented along the longitudinal direction while the third layer was oriented in the transverse direction. This pattern was repeated

throughout the layup. The 2x2 twill was used on the very top and bottom layers rotated at a 45 degree angle from the principle axis. (Expectation: Greater strength along longitudinal axis with some strengthening in the transverse direction)

Layup B: 2x2 carbon twill without any rotation between layers. Half the fibers were along the principle axis and the other half 90 degrees to the principle axis. The cross section of this layup had the same strength in the longitudinal direction as it did in the transverse. (Expectation: Strength in both the longitudinal and transverse direction)

Layup C: Unidirectional fibers all in the same direction along the principle axis, meaning all of the fiber strength was oriented in the longitudinal direction. (Expectation: Strength along the principal axis only, no fibers in the transverse direction).

In order to test the results of the FE model, we will create a new brace for the study team member and we will enroll 10 individuals who currently have a Gillette ankle foot orthosis and foot complication related to diabetes. Participants will attend an initial study visit when they will sign a consent and have a mold of their foot taken in order to design carbon fiber off loading brace.

Participant selection, Inclusion and Exclusion Criteria

Inclusion Criteria

1. Daily life includes a minimum of moderate activity level (variable cadence walking)
2. Have a Gillette or carbon off loading orthosis as a result of diabetes related foot impairments
3. Diagnosis of diabetes mellitus and peripheral neuropathy
4. Ability to ambulate in the community (K-level ≥ 2)
5. Age > 21 years

Exclusion Criteria (Must be a no)

1. Unable to ambulate and complete testing required for study participation.
2. Severe foot deformity of the hindfoot or any deformity of the foot with a dislocation resulting in a bony prominence on the plantar/weightbearing surface of the foot.
3. Neurological diseases that affects walking

Data Acquisition:

Participants who meet the inclusion/exclusion criteria will be identified by a member of the research team. A member of the research team will contact the participant to assess interest and schedule for testing. The first visit will begin with a member of the research team reading and explaining the informed consent document to the participant. After informed consent is obtained the research team member will create a mold of the participant's foot. The mold will be used in conjunction with the results from the FE model to create a new brace for the participant to be tested at a later date. The following tests will then be completed during the first visit:

- 1) Collection of medical and personal information: the participants will provide their and their doctor's contact information as well as medication list, a brief medical history, and information about activities of daily living.
- 2) Movement analysis: Reflective markers will be placed in various locations on the feet, legs, and body so we can record movements of the foot and leg while walking. We will place pressure sensing insoles into the participant's footwear to measure the amount of pressure when performing the activities listed during the recording. The participant will be recorded with the device or footwear while performing daily activities. The conditions under which they will walk with first will be randomized using a computer program which will generate a random order for the conditions. The recordings will be in a

format in which any information that identifies the participant is removed. The de-identified recording will be stored on a secure server, in a secured area behind locked doors. Only study personnel will have access to these computer files.

- 3) Questionnaires: Foot and Ankle Ability Measure and Quebec User Evaluation of Satisfaction with Assistive technology 2.0 questionnaire (asks questions about use, comfort, effectiveness, and professional services). The participant is free to skip any questions that they prefer not to answer.
- 4) Plantar pressure testing: the participant will be asked to walk across a surface barefoot. This test will occur during one of the study visits and will take place at [name] in the Applied Kinesiology Lab.
- 5) Neuropathy Assessment: Foot sensation will be measured using a monofilament and a biothesiometer. Monofilaments are similar to fishing line of different thicknesses, and will be placed on the bottom of the foot to test if the participant feels it touching the skin. A biothesiometer is a vibrating wand that will be placed on the bottom of the foot to test if the participant feels it.

Following the first visit, a new CFO will be fabricated based on the mold and on results from a FE model. The participant will pick up the orthosis at the offices of Orthotic and Prosthetic Design. The orthosis will be examined and modified for comfort. The participant will then wear the brace from 1 week. If the brace is causing discomfort or pain during this week the participant may return to have it modified. The participant will return to O & P Design after a week. If necessary, the brace will be adjusted to avoid any rubbing on the foot or ankle. The participant will then continue to wear the orthosis and can return to O & P Design at any time to have the brace examined and modified for comfort. Once the participant has worn the brace for two consecutive weeks with no issue, they will return to complete tests 1-5.

Statistical Analyses:

A repeated measures ANOVA will be used to test for differences of the primary measure of peak plantar pressure at the forefoot, midfoot, and heel during walking while the participants are barefoot, wearing the CFO consistent with current clinical standards, and wearing the new CFO fabricated based on the results of the FE model. Statistical significance was set at $p < 0.05$.

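### Goal 2 ranks the three layups for fracture propensity on stress alone, although the plan says their directional strengths differ, so it can tie or misorder them.

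*Combined protocol and SAP*

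**What the plan says.** The section Model Execution / CFO Design Characteristic Perturbation states two goals for comparing layups A, B and C. The first is to maximise deflection, as an indirect measure of energy return. The second is a brace that "minimized stress within the brace (i.e. indirect measure of propensity for strut fracture and failure". On the conditions of the comparison it says: "The three CFC were each modeled with the same geometry (equal length and thickness), boundary conditions, and loading conditions".

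The same section says that during fabrication "layers of CFC are added one at a time in varying directions depending on in which direction strength is needed", and it describes each layup by its strength:

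- **A:** mostly longitudinal unidirectional layers with some transverse ones, and 45-degree twill on the two faces. Strength is expected mainly along the length, with some across.
- **B:** twill throughout, with its fibers split evenly between the two directions. On the resulting strength the plan says: "The cross section of this layup had the same strength in the longitudinal direction as it did in the transverse".
- **C:** unidirectional along the length. "Strength along the principal axis only, no fibers in the transverse direction".

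Model Development names deflection and stress as the model outputs. On inputs it says: "Material properties for the CFC and CFC-to-CFC layer interfaces will be derived from the manufacturer specifications and from prior investigations by our group". On checking it says: "These results will be cross referenced with a simple beam bending equation to confirm accuracy". No part of the document divides stress by strength or names a failure index, a strength limit or a mechanical failure test. Data Acquisition says that each participant's new orthosis is made from the mold and the finite element (FE) results.

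**The concern.** Failure depends on stress relative to strength. Within one material, lower stress means a larger margin. Across layups that differ in strength by direction, it need not. Strength informed which layups became candidates, but it does not enter the goal that compares them.

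Holding geometry, supports and load equal sharpens the problem. In simple bending of a uniform section, stress is fixed by load and geometry and does not depend on the material. Stress alone may then fail to separate layups that differ in closeness to failure, while deflection still favours the more flexible one.

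What is at stake is the choice of device. The FE results feed into the brace, which participants wear for at least two weeks before retesting. Goal 2 is the only stated goal that addresses strut fracture.

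**Working it through.** The document gives no stress, modulus or strength value, so there is no figure to reproduce. What follows is an illustration. From the document come equal geometry and load, B's half share of longitudinal fibers, A's stacking pattern, and the beam equation as the planned check. All property ratios are assumptions.

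**1. Homogenised twill, B against C.** Set C's longitudinal modulus and strength to 1. Stress = Mc/I and cantilever deflection = PL³/(3EI). Take P = 1, L = 10, b = h = 1, so I = 1/12.

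- Stress: 10 × 0.5 ÷ (1/12) = 60 for both layups, a ratio of 1.0.
- Deflection: 4000/E, which is 4000 for C (E = 1) and 8000 for B (E = 0.5), a ratio of 2.0.
- Longitudinal stress/strength, if B's strength is 0.5: 1.0/0.5 = 2.0 times C's.

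Ranges use three assumptions: transverse/longitudinal modulus r = 0.05 to 0.15, a twill factor on stiffness k = 0.85 to 1.0, and a twill factor on strength of 0.8 to 1.0.

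- B's modulus is k(1 + r)/2: from 0.85 × 1.05/2 = 0.446 to 1.15/2 = 0.575. Relative deflection is 1/0.575 = 1.74 to 1/0.446 = 2.24.
- B's strength runs from 0.8 × 0.5 = 0.40 to 1.15/2 = 0.575. Relative stress/strength is 1/0.575 = 1.74 to 1/0.40 = 2.50.

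On this reading B ties C on stress and wins on deflection, whatever their strengths.

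**2. The order could also go the other way.** C has no transverse fibers. Suppose its transverse strength is 2 to 5% of its longitudinal strength. Its transverse stress/strength then equals B's longitudinal 1.74 to 2.50 once transverse stress is 1.74 × 0.02 = 3.5% to 2.50 × 0.05 = 12.5% of C's longitudinal stress. Simple bending produces no transverse stress, so this is only a break-even point.

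**3. Ply-resolved stress, B against C.** If stress is read in B's longitudinal fibers, it is 1/E relative to C, which is 1.74 to 2.24. The tie disappears, and stress alone already gives the same longitudinal order as stress/strength.

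**4. Ply-resolved stress, layup A.** Ply stress = ply modulus × curvature × distance from the neutral axis. Take repeated 0/0/90 layers between 45-degree twill faces, with 14 to 32 plies, r = 0.05 to 0.10, 45-degree twill modulus 0.12, and transverse strength 2 to 5% of longitudinal.

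| Layup A | Longitudinal plies | Transverse plies |
|---|---|---|
| Peak stress, relative to nominal | 1.53 to 1.72 | 0.08 to 0.19 |
| Stress/strength | 1.53 to 1.72 | at least 1.66 |

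Within every case run, the transverse plies have the higher stress/strength. The narrowest case is 32 plies with r = 0.05 and transverse strength 5%: 0.083/0.05 = 1.66 against 1.56. So the most stressed ply need not be the one nearest its strength. This order relies on the assumed modulus ratio being at least as large as the assumed strength ratio. Shear and interlaminar failure were not computed.

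**The case against.** The strongest objection is that the tie between B and C depends on a modelling choice that the document does not state. Properties are assigned to the interfaces between layers, which suggests a layer-resolved model, although the text does not say how a twill layer is represented. With fiber-level stress, goal 2 orders B and C correctly in the longitudinal direction. Likewise, if the unidirectional layers of A and C are the same material, raw longitudinal ply stress orders those two as a strength ratio would. All of this stands, and it limits the longitudinal concern to a homogenised twill. It does not settle transverse or interlaminar failure.

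The beam equation is planned only as a cross-check of an FE model with a traced profile and a moving load. That also stands: the figures above illustrate the goal and do not predict the planned model's output. A reader might infer that the plan will select B over C whatever their strengths. The document does not support this, because it gives no properties, does not say which stress is read, and includes a third layup.

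The plan calls stress an indirect measure, and the manufacturer's specifications may include strength. The first admits a proxy without making it comparable across layups. The second does not bring strength into the stated goal.

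A reader might also ask for a rule, fixed in advance, for conflict between deflection and fracture risk. That is a separate matter, and the past tense of parts of the section means the results may already be known.

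**Conclusion.** The point holds as a weakness in the comparison criterion. Goal 2 uses stress alone to rank layups that the plan itself describes as differing in directional strength, so it can tie or misorder them. No misranking of the three is shown.

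The size depends on how stress is read. With a homogenised twill, B and C tie on stress, while B's longitudinal stress/strength is about 1.7 to 2.5 times C's. With ply-resolved stress the longitudinal order is right, and what remains is transverse and interlaminar failure, whose size cannot be fixed from the document. Every ratio beyond the half share of fibers is assumed. The layup A result concerns transverse ply cracking, which is not the same as fracture of the strut.

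A reader might infer that the trial's main comparison is compromised or that the brace will fracture. Neither follows. Fracture is not an endpoint, the repeated measures ANOVA of peak plantar pressure is unaffected, and no predicted failure is shown. The finding does not say which layup should be used.

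**What to change.** Replace goal 2 with minimising the peak ratio of stress to strength in the corresponding direction, over the whole stance phase. Report it separately for longitudinal, transverse and, where the model outputs it, interlaminar stress. Keeping the directions apart matters because a single maximum would mix transverse ply cracking with fracture of the strut. State also how the twill layers are represented.

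The same three FE models can serve, with no burden on participants. There are two costs. Directional strength values may have to be requested from the manufacturer, since the document does not say whether the specifications in use include them. Ply-level stress output must also be available, which the document does not confirm.

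### Is the clinical-standard orthosis condition in the ANOVA mixed or mislabelled because the plan never ties it to the brace participants already own?

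*Combined protocol and SAP*

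**What the plan says.** The device is described in four places in the combined protocol and SAP.

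- **Model Development.** One CFO is to be "fabricated for a study team member using the geometry consistent with the clinical standard" at a named orthotics provider. It is the baseline for the finite element model. The section lists the parts of a CFO: a carbon composite strut, a leather calf support, and a shoe of leather and foam.
- **Design text before the eligibility criteria.** "we will enroll 10 individuals who currently have a Gillette ankle foot orthosis", together with a diabetic foot complication.
- **Inclusion criterion 2.** "Have a Gillette or carbon off loading orthosis as a result of diabetes related foot impairments".
- **Statistical Analyses.** The repeated measures ANOVA has three walking conditions: barefoot, "wearing the CFO consistent with current clinical standards", and the new CFO built from the model results.

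The Data Acquisition section describes the test itself only in general terms: "The participant will be recorded with the device or footwear while performing daily activities". The information collected at the first visit includes "medication list, a brief medical history, and information about activities of daily living", and the list has no entry for orthosis type. The only brace the plan makes for participants is the new one.

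**The concern.** The analysis names a comparator that the plan does not supply to anyone in the trial. The one clinical-standard CFO it fabricates belongs to a study team member. By inference the comparator is the orthosis each participant brings along, yet the two descriptions of that orthosis differ, and neither is linked to the name used in the analysis. If Gillette and carbon braces are different devices, the middle condition could hold both, or could hold none of the kind it is named after.

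The new-versus-existing contrast is the one that tests the redesign; the barefoot contrast shows only that a brace changes pressure. With 10 participants, each supplies one tenth of the comparator mean. A result reported as new CFO against standard CFO would then answer a somewhat different question from the one stated.

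**Working it through.** The plan gives no figure to reproduce on this point: the sample of 10 comes without a power calculation, effect size or standard deviation. The check is a comparison of texts, followed by a short piece of algebra.

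**Step 1: which device is the comparator?** No sentence says. Two facts narrow it down. The new brace is made only after the first visit, and participants receive no other brace from the study. Any orthosis worn for the first-visit movement and in-shoe pressure tests is therefore, on the likeliest reading, the participant's own. This is inference, but no sentence contradicts it.

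**Step 2: do the two descriptions conflict?** The design text mentions only a Gillette; criterion 2 mentions a Gillette or a carbon off-loading orthosis. There are two readings.

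- *One class of device.* Criterion 2 groups two names for the qualifying brace, and the analysis paragraph calls the same brace a CFO. The comparator is uniform.
- *Two types of device.* Criterion 2 is wider than the design text, and the comparator may be mixed.

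The text does not decide between them. Nor is Gillette against carbon certain to be the right dividing line: Model Development ties the clinical standard to the geometry used at one provider, so a carbon brace of another geometry could also fall outside it.

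**Step 3: what would a mix do to the estimate?** For participant i, write new, own and std for peak pressure in the new brace, in the participant's own brace and in a hypothetical clinical-standard CFO. Then

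new_i − own_i = (new_i − std_i) − (own_i − std_i).

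Averaging over 10 participants, of whom k own something other than the standard CFO:

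mean(new − own) = mean(new − std) − (1/10) × [sum of (own_i − std_i) over those k participants].

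The left side is an unbiased estimate of new brace against current orthosis for every k. Only its reading as new against standard depends on the last term. For k = 0 that term is zero. For k = 10 it is the full average gap between the two kinds of device. The documents give neither k nor the size or sign of the gap, so the term cannot be put into numbers, and the full range of k from 0 to 10 applies.

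**Step 4: what would a mix do to precision?** This needs assumed values. If the within-person contrast differed between two device groups by D standard deviations, with a share p in one group, the standard deviation of the differences would be multiplied by √(1 + p(1 − p)D²). For an even split:

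- D = 0.5: √(1 + 0.25 × 0.25) = 1.031
- D = 1: √(1 + 0.25 × 1) = 1.118

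The loss is at most about 12% under these assumptions. Renaming the condition or recording the device would not remove it.

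**Step 5: would the device type be lost?** Criterion 2 makes ownership of a named orthosis a condition of entry, so staff must establish which device each person has. Staff also place pressure-sensing insoles in the participant's footwear and record the participant walking. The first-visit list is a summary, not a case report form. Its silence does not show that the type goes unrecorded, although the plan does not guarantee that it is recorded.

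**The case for a change.** The best argument for a change is that it costs almost nothing and works under either reading. If a Gillette is the clinical-standard CFO, one sentence closes the matter. If it is not, calling the condition the participant's current orthosis and noting the type at the first visit makes the conclusion match the data. Device details are easiest to capture when the person is in the room, and with 10 participants even a few different braces would matter to interpretation.

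Part of this stands. The two descriptions are not aligned, Gillette is undefined, and a report should name the comparator for what it was. The argument does not show a fault in the design or the analysis. It leaves the participants, the conditions, the measurements and the ANOVA as they are. It rests on a difference between devices that the documents neither state nor size. Breaking the results down by device in a group of 10 would be no more than a listing.

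**Conclusion.** This is a gap in terminology that the team can fill sensibly, and it calls for no change to the plan. The documents show an undefined term and a comparator whose source is left unstated. They do not show a mixed or mislabelled comparator: the number affected may be 0 of 10, and any shift in meaning is of unknown size and sign.

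The conclusion rests on two assumptions. The first is that the comparator is the participant's own orthosis, which is the likeliest reading because the study makes no other brace for participants before the new one. The second is that staff who screen on criterion 2 and test the device know what it is. Under these, the within-person comparison of new brace with existing orthosis holds whatever the mix, and the report need only describe the comparator as the device actually worn. A claim about the clinical-standard CFO in particular would depend on the participants' own braces being of that kind.

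### Walking order is randomised with no balance specified and no order term in the ANOVA, which with 10 participants costs precision if there is any order effect

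*Combined protocol and SAP*

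**What the plan says.** The trial is small: "we will enroll 10 individuals who currently have a Gillette ankle foot orthosis". Under Data Acquisition, test 2 (Movement analysis), the order in which the conditions are walked "will be randomized using a computer program which will generate a random order for the conditions". The text does not say whether orders are balanced across participants, and it does not list the conditions being ordered.

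Under Statistical Analyses, "A repeated measures ANOVA will be used to test for differences of the primary measure of peak plantar pressure" at three foot regions. The conditions are "barefoot, wearing the CFO consistent with current clinical standards, and wearing the new CFO fabricated based on the results of the FE model". No term for order, period, sequence or visit is named. The threshold is p < 0.05.

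Three statements limit what the random order can cover:

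- The new brace does not exist at the first visit: "Following the first visit, a new CFO will be fabricated based on the mold and on results from a FE model".
- After the wear period participants come back, and "they will return to complete tests 1-5". Test 2 and its random order are therefore repeated, but the text does not say whether the standard brace is walked again.
- The barefoot walk is a separate item (test 4): "This test will occur during one of the study visits".

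**The concern.** The plan treats walking order as important enough to randomise, but carries it no further. Warm-up, fatigue, or drift and re-seating of the insoles can make a later walk differ from an earlier one. If the orders are simple random draws, 10 people will often split unevenly, and the single realised comparison then carries part of the order effect. Even with an even split, an ANOVA without an order term leaves the order effect in the residual. At stake is the precision of a comparison that has only 10 participants and no stated power calculation.

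**Working it through.** **Inputs.** From the documents: n = 10, a random order, a repeated measures ANOVA with no order term, and a 0.05 level. The documents give no SD, target difference or order effect, so there is no planned power figure to reproduce. Assumed: a true difference of 1 SD of the within-participant difference between two conditions; an order shift π of 0, 0.25, 0.5 or 1.0 of that SD; a two-sided test.

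**Chance imbalance.** If each person's order of two conditions is an independent fair draw, the count follows Binomial(10, 0.5):

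- exactly 5-5: 252/1024 = 24.6%
- 7-3 or worse: 2 × (120 + 45 + 10 + 1)/1024 = 352/1024 = 34.4%
- 8-2 or worse: 2 × (45 + 10 + 1)/1024 = 112/1024 = 10.9%

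**Effect on the estimate.** Write the paired difference as δ + o·π + e, with o = ±1 by order and e of SD 1. The order contribution to the mean is π times the mean of o. That mean averages 0, with SD 1/√10 = 0.316, so there is no bias over repeated draws. An 8-2 split shifts the estimate by (8 − 2)/10 × π = 0.6π. The standard error rises by the factor √(1 + π²): 1.03, 1.12 and 1.41 for π = 0.25, 0.5 and 1.0.

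**Type I error.** With simple random order and no order term, simulation (200,000 runs) gives 4.9%, 5.0%, 5.1% and 5.2% for π = 0, 0.25, 0.5 and 1.0.

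**Power (%)**, δ = 1, same simulation; t test on 9 df without the term and 8 df with it:

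| π | Simple random, no term | 5-5, no term | Simple random, with term | 5-5, with term |
|---|---|---|---|---|
| 0 | 80.3 | 80.3 | 74.3 | 79.1 |
| 0.25 | 78.0 | 78.3 | 74.3 | 79.2 |
| 0.5 | 70.9 | 72.0 | 74.2 | 79.0 |
| 1.0 | 50.0 | 48.3 | 74.3 | 79.1 |

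Balance alone does almost nothing, because the order effect still inflates the estimated variance: its expectation is 1 + (10/9)π², or 2.11 at π = 1. The term alone gives about 74% whatever the order effect, because the adjusted variance is multiplied by 1/(1 − m²), with m the mean of o. At 8-2 that is 1/(1 − 0.36) = 1.56, a 25% larger standard error. Only the two together hold power at 79%.

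**Three conditions.** As an illustration, suppose all three ANOVA conditions shared one random order, with a linear position effect of g residual SDs per step. Residual variance becomes 1 + g²: 1.06, 1.25 and 2.00 for g = 0.25, 0.5 and 1.0. Simulated type I error stays at 4.9% to 5.1% (100,000 runs). If one condition differs by 1 residual SD, power is 55.9%, 52.8%, 46.1% and 29.8% for g = 0, 0.25, 0.5 and 1.0.

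**The case against.** Omitting order from the analysis of a randomised-order comparison is valid on average, so this is a refinement and not a correction of an error. That stands.

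A reader might infer something stronger: that the plan biases the brace comparison or exceeds its 5% level. The documents do not support this. Given an 8-2 split, type I error would be about 10% at π = 0.5 and 20% at π = 1.0. Against that, at 5-5 the test is conservative (about 3% and under 1%), and 5-5 and 6-4 together cover 100 − 34.4 = 65.6% of draws. Over all draws the level is about 5%.

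A reader might also infer that the program draws orders without restriction. The text neither states nor excludes balancing. If the program already balances, that half of the point needs only a sentence; the missing order term remains.

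The size rests on assumptions. At π = 0.25 the loss is two points, and the fall to 50% needs an order shift as large as the whole SD of the paired difference. Nothing in the documents shows which value is realistic.

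The strongest objection is about scope. The new brace cannot be in the first visit's order, and the barefoot pressure test is described apart from it. The random order reaches the brace contrast only if both braces are walked at the return visit, which is not stated. This stands, and it limits what the fix can do.

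**Conclusion.** The point holds as a matter of precision. No balance is specified and no order term is planned, so with 10 participants an order effect would enlarge the error term, and uneven splits are common under simple randomisation. The cost runs from negligible to large: power of 78%, 71% or 50% against 79%, for assumed order shifts of 0.25, 0.5 or 1.0 SD and an assumed true difference of 1 SD. The remedy is cheap enough to be worth adopting without knowing the order effect.

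It does not show that the planned test is invalid. Nor does it settle the brace comparison. If the standard-brace data come from the first visit, brace is fully confounded with visit, and neither balanced orders nor an order term can separate them. In that case an assumed visit-to-visit shift of 0.25, 0.5 or 1.0 SD, always in the new brace's direction, would give a type I error of 11.0%, 29.3% or 80.5%.

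**What to change.** - **Data Acquisition, test 2:** state that orders are allocated in balance within each session. For two conditions this means 5-5. Three conditions have six orders and 10 is not a multiple of 3 or 6, so aim for as near balance as 10 allows.
- **Statistical Analyses:** add walking position to the repeated measures model, beside participant and condition.
- **Both sections:** list the conditions walked at each visit, including whether the standard brace is walked again at the return visit, and say which visit's data enter the ANOVA.

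Make the first two changes together, since neither alone gives the full gain.

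**Cost.** One setting in the randomisation program and one model term. The term uses one error degree of freedom with two conditions (9 to 8) or two with three conditions (18 to 16). If there is no order effect, power for two conditions goes from 80% to 79%. Dropout that breaks the balance adds a little: a 5-4 split multiplies the adjusted variance by 1/(1 − 1/81) = 1.012, besides the loss of the participant.
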